#### ***4.3.2.2.2. *Electrocardiograms (ECGs)****

ECG data will include heart rate, PR, QRS, QT, and corrected QT (QTc). The QTc data analysis will use the collected values based on Fridericia formula.

ECG values relative to PCI criteria, will be summarized by treatment group, ECG parameter and category.

#### ***4.3.2.2.3. *Clinical Laboratory Values****

The haematology and clinical chemistry laboratory data, relative to PCI criteria, will be summarized by treatment group, laboratory test and category.

#### ***4.3.2.2.4. *Vital Signs****

Vital sign data include temperature, systolic blood pressure (SBP), diastolic blood pressure (DBP), heart rate (HR), and respiratory rate.

Vital sign data (SMP, DBP and HR), relative to PCI criteria, will be summarized by treatment group, vital sign and category. Worst-Case Vital Sign Results Relative to Normal Range Post-Baseline Relative to Baseline will also be summarized.

### **4.4. Other Safety Analyses**

The safety analyses will be based on the Safety Analysis Set, unless otherwise specified.

#### **4.4.1. Additional Safety Assessments**

##### **4.4.1.1. Laboratory Data**

In addition to laboratory summaries related to PCI criteria, summaries of worst-case grade increase from baseline will be provided for all the lab tests that are gradable by CTCAE v4.03. These summaries will display the number and percentage of subjects with a maximum post-baseline grade increasing from their baseline grade. Any increase in grade from baseline will be summarized along with any increase to a maximum grade of 3 and any increase to a maximum grade of 4. Missing baseline grade will be assumed as grade 0. For laboratory tests that are graded for both low and high values, summaries will be done separately and labelled by direction, e.g., sodium will be summarized as hyponatremia and hypernatremia separately.

Change from period baseline values of haematology and chemistry will be summarized using descriptive statistics.

For lab tests that are not gradable by CTCAE v4.03, summaries of worst-case changes from baseline with respect to normal range will be generated. Decreases to low, changes to normal or no changes from baseline, and increases to high will be summarized for the worst-case post-baseline. If a subject has a decrease to low and an increase to high during the same time interval, then the subject is counted in both the “Decrease to Low” categories and the “Increase to High” categories.

Separate summary tables for haematology and chemistry laboratory tests will be produced. Liver function laboratory tests will be included with chemistry lab tests.

Protocol-required routine urinalysis tests will also be summarized descriptively.

An e-DISH plot of maximum post baseline total bilirubin versus maximum post baseline ALT will be created.

##### **4.4.1.2. Vital Signs**

In addition to above summaries of PCI criteria, summary statistics for all results and changes from period baseline will be provided by day of assessment for each test.

##### **4.4.1.3. ECG**

ECG findings are defined from best to worst as: “normal”, “abnormal - not clinically significant”, and “abnormal - clinically significant”. The worst finding will be selected at each time point when there is repeat ECG. All ECG findings will be summarized by days.

The QTc data analysis will use the collected values based on Fridericia formula.

The QTc values based on Fridericia formula will be rounded to the integer and the values will be categorized into the following CTCAE grade and ranges: Grade 0 (<450 msec), Grade 1 (450-480 msec), Grade 2 (481-500 msec), and Grade 3 ( $\geq 501$  msec). Summaries of grade increase will be provided. These summaries will display the number and percentage of subjects with any grade increase, increase to grade 2 and increase to grade 3 for the worst-case post-baseline only. Missing baseline grade will be assumed as grade 0.

The changes in QTc values will be categorized into the clinical concern ranges which are specific to changes in QTc: 31-60 and  $>60$  msec. A summary of change in QTc value will display the number and percentage of subjects with a change within each range for the worst-case post-baseline only. Subjects with missing baseline values will be excluded from this summary.

A figure plotting the baseline QTc and the worst-case post-baseline values will be produced for each period. The figure will have reference lines at 450, 480 and 500 msec for both the x and y axes. There will be diagonal reference lines at equality (i.e. a 45-degree line), at equality plus 30 msec, and at equality plus 60 msec.

## **4.5. Other Analyses**

### **4.5.1. Subgroup analyses**

There will be no subgroup analysis planned.

### **4.5.2. Analyses to Support Regional Submission**

There will be no regional submission planned.

## **4.6. Interim Analyses**

There will be no interim analysis performed.

## **4.7. Changes to Protocol Defined Analyses**

There were no changes or deviations to the originally planned statistical analysis specified in the original version of protocol (Dated: 06 Nov 2023).

## **5. SAMPLE SIZE DETERMINATION**

From the Adjusted gMean ratios and 90% CIs reported in the historical reference [Vonk, 2022], CVw(%) has been obtained using the CVfromCI function from POWERTOST package in R software. The R CVfromCI function uses methodology described in Section 5.1.1. CVw(%) values of 11.5%, 12.5%, 14.9%, 17.9% for EE AUC(0-inf), EE Cmax, LNG AUC(0-inf) and LNG Cmax respectively were calculated (Table 4). The largest CVw for the analytes and parameters is 17.9%.

**Table 4: Intrasubject Coefficient of Variability (CVw%) for PK Parameters of EE and LNG**

Historical Reference	Analyte	Parameter	n	Adjusted gMean ratio	(90% CI)	CVw%
Madelon C. Vonk, et al.	EE	AUC (0-inf)	15	101.2	(94.0, 109.1)	11.5
		C max	15	116.7	(107.6, 126.5)	12.5
	LNG	AUC (0-inf)	15	88.1	(80.0, 97.0)	14.9
		C max	15	100.9	(89.9, 113.2)	17.9

The true ratio of Microgynon+GSK3036646 versus Microgynon alone, is assumed to be 1.0 for all 4 comparisons, EE AUC(0-inf), EE Cmax, LNG AUC(0-inf) and LNG Cmax. In order to calculate the joint power for the four comparisons, a conservative between parameter correlation of 0.6 has been assumed; of note considering correlation of 1.0 would increase the joint power by less than 1% for the same sample size. Based on these assumptions an evaluable sample size of 16 provides 92% (Table 5) joint power to ensure that the 90% CIs for the geometric mean ratios for all parameters lie within the range of 0.8 to 1.25. To account for an expected 20% rate of non-evaluatable participants, approximately 20 participants will be enrolled to ensure at least 16 participants provide evaluable data in both test and reference periods.

**Table 5: Estimated Power and Sample Size Table**

Analyte	Parameter	n	CVw%	Power
EE	AUC (0-inf)	16	11.5	99.98
	C max	16	12.5	99.87
LNG	AUC (0-inf)	16	14.9	98.66
	C max	16	17.9	92.73
Joint Power for all 4 comparisons		16		91.91

Table 6: provides the 90% CIs for a range of possible observed ratios, for each assumed CVw%, with 16 estimated participants.

**Table 6: Sample Size: Estimated Precision for Different Observed Effects**

Analyte	Parameter	n	CVw%	Observed Ratio	Estimated 2-sided 90% CI
EE	AUC (0-inf)	16	11.5	0.90	(0.84, 0.97)
				1.0	(0.93, 1.07)
				1.10	(1.02, 1.18)
	C max	16	12.5	0.90	(0.83, 0.97)
				1.0	(0.93, 1.08)
				1.10	(1.02, 1.19)

Analyte	Parameter	n	CVw%	Observed Ratio	Estimated 2-sided 90% CI
LNG	AUC (0-inf)	16	14.9	0.90	(0.82, 0.99)
				1.0	(0.91, 1.10)
				1.10	(1.00, 1.21)
	C max	16	17.9	0.90	(0.81, 1.01)
				1.0	(0.90, 1.12)
				1.10	(0.98, 1.23)

### 5.1.1. Calculation of CVw from CI:

The point estimate (PE, adjusted geometric mean) and the confidence interval limits have been obtained from historical reference.

The number of subjects / sequence (example 2×2 cross-over), is obtained as follows:

- If total sample size (N) is an even number, assume  $n_1 = n_2 = \frac{1}{2}N$
- If N is an odd number, assume  $n_1 = \frac{1}{2}N + \frac{1}{2}$ ,  $n_2 = \frac{1}{2}N - \frac{1}{2}$  (not  $n_1 = n_2 = \frac{1}{2}N$ )

The difference between the CL and the PE can be calculated as follows on the log-scale (using the CL which is given with the highest number of significant digits).

$$\Delta_{CL} = \ln (CL_{hi}) - \ln(PE) \text{ or } \Delta_{CL} = \ln(PE) - \ln (CL_{lo})$$

The Mean Square Error (MSE) is then calculated as follows:

$$MSE = 2 \left( \frac{\Delta_{CL}}{\sqrt{\left( \frac{1}{n_1} + \frac{1}{n_2} \right) \times t_{(1-2\alpha, n_1+n_2-2)}}} \right)^2$$

And finally, the CVw is calculated from the MSE:

$$CVw\% = 100 \times \sqrt{(e^{MSE} - 1)}$$

## 6. SUPPORTING DOCUMENTATION

### 6.1. Appendix 1 Study Population Analyses

Unless otherwise specified, the study population analyses will be based on the Enrolled Analysis Set. A summary of the number of participants in each of the participant level analysis set will be provided.

Screen failure participants will be summarized based on Screened analysis set.

### **6.1.1. Participant Disposition**

A summary of the number and percentage of participants who completed the study as well as those who prematurely withdrew from the study will be provided. Reasons for study withdrawal will be summarized.

A summary of study intervention status will be provided. This display will show the number and percentage of participants who have completed the scheduled study intervention, or have discontinued study intervention prematurely, as well as primary reasons for discontinuation of study intervention.

### **6.1.2. Demographic and Baseline Characteristics**

The demographic characteristics including age, gender, ethnicity, height/weight at screening and race will be summarized with descriptive statistics based on the Enrolled Analysis Set.

Past medical conditions and current medical conditions as of screening will be summarized respectively. Substance use, including smoking history, tobacco use, alcohol and drug history will be summarized.

### **6.1.3. Protocol Deviations**

Important protocol deviations will be summarized.

Protocol deviations will be tracked by the study team throughout the conduct of the study. These protocol deviations will be reviewed to identify those considered as important as follows:

- Data will be reviewed prior to freezing the database to ensure all important deviations are captured and categorised in the protocol deviations ADaM dataset.
- This dataset will be the basis for the summaries of important protocol deviations.

### **6.1.4. Prior and Concomitant Medications**

Concomitant medications will be coded using both the GSK Drug and WHO Drug dictionaries. However, the summary will be based on GSK Drug dictionary only. The summary of concomitant medications will be provided by ingredient, i.e. multi-ingredient medications will be summarized for each individual ingredient rather than a combination of ingredients. The summary will be created using ingredient base names, i.e. ingredients with the same base name but different salt will appear under one base name in the summary. Anatomical Therapeutic Chemical (ATC) classifications will not appear in the summary.

For classifying study phase for concomitant medication, use the following definition.

Medication Classification	Definition
Prior	If medication end date is not missing and is on or prior to the date of the screening visit
Concomitant	Any medication that is not a prior
Please refer to Section 6.2.8 : for handling of partial end dates for concomitant medication.	

### 6.1.5. Study Intervention Compliance

A summary of treatment compliance of Microgynon and GSK3036656 based on the exposure data will be produced. Overall compliance categories will also be summarized using descriptive statistics, refer to OPS for more details.

## 6.2. Appendix 2 Data Derivations Rule

### 6.2.1. Change from Baseline

The change from baseline will be calculated by subtracting the period baseline values from the subsequent post-baseline values. If either the baseline or post-baseline value is missing, the change from baseline is set to missing as well.

### 6.2.2. Pharmacokinetic Parameters

For the purposes of calculating summary statistics and for statistical analysis, all PK parameters with the exception of  $T_{max}$ ,  $t_{1/2}$  will be  $\log_e$  transformed.

Between subject coefficient of variation  $\%CV_b$  will be calculated according to the following methods:

Untransformed Data :  $\frac{SD}{mean} \times 100$ ,

Transformed Data :  $\sqrt{e^{S^2} - 1} \times 100$ ,

where S is the SD of the  $\log_e$  transformed data,  $S^2$  = variance of  $\log_e$  transformed data.

### 6.2.3. Criteria for Potential Clinical Importance

Reference ranges for all laboratory parameters collected throughout the study are provided by the laboratory. A laboratory value that is outside the reference range is considered either high abnormal (value above the upper limit of the reference range) or low abnormal (value below the lower limit of the reference range). Note: a high abnormal or low abnormal laboratory value is not necessarily of clinical concern.

National Cancer Institute Common Terminology Criteria for Adverse Events [NCI-CTCAE v4.0.3] will be used to assign grades to the relevant laboratory parameters, blood pressure and QTc.

In addition, the following criteria will be used to flag potential clinical importance (for laboratory data, ECG parameters and vital signs):

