**Adverse Events/ Serious Adverse Events, Clinical laboratory assessments, ECG, and Vital Sign measurements:**

- Population: Healthy female participants of non-childbearing potential aged 18 to 65 years.
- Endpoints:
  - Incidence of serious adverse events within each treatment period.
  - Incidence of adverse events of grade 3 severity or higher within each treatment period.
  - Incidence of adverse events considered by the investigator to be possibly, probably or definitely related to study drug (overall and separately for Microgynon and GSK3036656) within each treatment period.
  - Incidence of participants withdrawn from the treatment/study due to adverse events within each treatment period.
  - Incidence of ECG values of PCI within each treatment period.
  - Incidence of clinical chemistry laboratory values of PCI within each treatment period.
  - Incidence of haematology laboratory values of PCI within each treatment period.
  - Incidence of vital signs parameters of SBP, DBP and HR of PCI within each treatment period.
- Treatments: single dose Microgynon, once daily GSK3036656 and single dose Microgynon +once daily GSK3036656
- Strategy for intercurrent event: The intercurrent events of interest are participants missing the dose of Microgynon, missing one or more doses of GSK3036656 or discontinuing GSK3036656 early due to any reason. The strategy for handling these intercurrent events will be a Treatment Policy Strategy, where all safety data after the intercurrent event will be included.
- Population-level summary: Frequency and percentage of participants; with the denominator for percentages being the number of participants entering the treatment period.

Rationale for estimand: It is important to document all safety issues that could potentially be attributable to the regimen, regardless of treatment non-compliance/discontinuation.

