### **5.2.2. Laboratory Assessments**

2. Presence of hepatitis B surface antigen at Screening or within 3 months prior to starting study treatment.
3. Positive hepatitis C antibody test result at Screening or within 3 months prior to starting study treatment AND positive on reflex to hepatitis C RNA.
4. Positive HIV-1 and -2 antigen/antibody immunoassay at Screening.
5. Alanine aminotransferase (ALT)  $>1.5 \times \text{ULN}$ . A single repeat of ALT is allowed within a single screening period to determine eligibility.
6. Bilirubin  $>1.5 \times \text{ULN}$  (isolated bilirubin  $>1.5 \times \text{ULN}$  is acceptable if bilirubin was fractionated and direct bilirubin  $<35\%$ ).

7. Any acute laboratory abnormality at Screening which, in the opinion of the investigator, should preclude participation in the study of an investigational compound.
8. Participants with haemoglobin <8.0 g/dL
9. Any Grade 2 to 4 laboratory abnormality at Screening, with the exception of creatine phosphokinase and lipid abnormalities (e.g., total cholesterol, triglycerides, etc), and ALT (described above), excludes a participant from the study unless the investigator provided a compelling explanation for the laboratory result(s) and has the assent of the sponsor. A single repeat of any laboratory abnormality is allowed within a single screening period to determine eligibility.
10. A positive test result for drugs of abuse (including marijuana), alcohol, or cotinine (indicating active current smoking) at Screening or before the first dose of study treatment.

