## Primary estimand of secondary Safety endpoints

### For all secondary safety endpoints the primary clinical question of interest:

[figure not shown]
Are GSK3036656 and Microgynon, taken separately or together, safe and well tolerated in healthy female participants of non-childbearing potential aged 18 to 65 years, regardless of study treatment discontinuation and the level of compliance of either treatment?

The primary estimands for Safety are described by the following attributes:

- Population: Healthy female participants of non-childbearing potential aged 18 to 65 years.
- Endpoints:
  - Incidence of serious adverse events within each treatment period.
  - Incidence of adverse events of grade 3 severity or higher within each treatment period.
  - Incidence of adverse events considered by the investigator to be possibly, probably or definitely related to study drug (overall and separately for Microgynon and GSK3036656) within each treatment period.
  - Incidence of participants withdrawn from the treatment/study due to adverse events within each treatment period.
  - Incidence of ECG values of PCI within each treatment period.
  - Incidence of clinical chemistry laboratory values of PCI within each treatment period.
  - Incidence of haematology laboratory values of PCI within each treatment period.
  - Incidence of vital signs parameters of SBP, DBP and HR of PCI within each treatment period.
- Treatments: single dose Microgynon, once daily GSK3036656 and single dose Microgynon +once daily GSK3036656
- Strategy for intercurrent event: The intercurrent events of interest are participants missing the dose of Microgynon, missing one or more doses of GSK3036656 or discontinuing GSK3036656 early due to any reason. The strategy for handling these intercurrent events will be a Treatment Policy Strategy, where all safety data after the intercurrent event will be included.
- Population-level summary: Frequency and percentage of participants; with the denominator for percentages being the number of participants entering the treatment period.

Rationale for estimand: It is important to document all safety issues that could potentially be attributable to the regimen, regardless of treatment non-compliance/discontinuation.

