##### **4.3.2.2. Main analytical approach**

All safety analyses will be performed on the Safety Population. Safety data will be presented in tabular format by treatment groups (Microgynon, GSK3036656 and Microgynon+GSK3036656) and summarized descriptively according to GSK's Integrated Data Standards Library. For each treatment group, the denominator for percentages (N) will be the number of participants entering the associated treatment period. No formal statistical analysis of the safety data will be conducted. Unless otherwise specified, available data will be analyzed as collected regardless of intercurrent events that may occur (treatment policy). Missing data will not be imputed.

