### 6.2.3.1. Laboratory Values

Haematology				
Laboratory Parameter	Units	Category	Clinical Concern Range	
			Low Flag (< x)	High Flag (>x)
Hematocrit	Ratio of 1	Male		0.54
		Female		0.54
		Change from Baseline	Decrease of 0.075	
Haemoglobin	g/L	Male	75	180
		Female	75	180
		Change from Baseline	Decrease of 25	
Lymphocytes	x10  / L		0.8	
Neutrophil Count	x10  / L		1.5	
Platelet Count	x10  / L		100	550
Red blood cell (RBC) count	million/mcL		4.2	6.1
Mean corpuscular volume (MCV)	fl.		80	100
Mean corpuscular hemoglobin (MCH)	picograms (pg)		27.5	33.2
%Reticulocytes	%		0.5	2
Monocytes	%		2	8
Eosinophils	%		1	4
Basophils	%		0.5	1
Clinical Chemistry				
Laboratory Parameter	Units	Category	Clinical Concern Range	
			Low Flag (< x)	High Flag (>x)
Calcium	mmol/L		2	2.75
Creatinine	%	Change from Baseline		Increase of 30%
Glucose	mmol/L		3	11
Potassium	mmol/L		3	5.5
Sodium	mmol/L		130	150
Direct bilirubin	mg/dl		<0.3	<0.3
Total protein	g/dl		6	8.3
Blood urea nitrogen (BUN)/Urea	mg/dl		5	20

Haematology				
Laboratory Parameter	Units	Category	Clinical Concern Range	
			Low Flag (< x)	High Flag (>x)
Creatine phosphokinase (CPK)	mcg/l		10	120
Homocysteine	µmol/L		4	14
Antiphospholipid antibodies	MPL		0	39.9
Sex hormone binding globulin (SHBG)	nmol/L		18	144

Liver Function				
Test Analyte	Units	Category	Clinical Concern Range	
ALT	IU/L	High	$\geq 3x$ ULN	
AST	IU/L	High	$\geq 3x$ ULN	
T Bilirubin	µmol/L	High	$\geq 1.5x$ ULN	

ULN = Upper Limit of Normal; ALT=Alanine Aminotransferase; AST=Aspartate Aminotransferase;

T. Bilirubin=Total Bilirubin

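### Most laboratory PCI flags ignore baseline, so a stable pre-existing value counts as an event in every treatment period (minor)

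*SAP*

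**What the plan says.** Protocol section 3 and SAP 1.1 list the same two laboratory endpoints: "Incidence of haematology laboratory values of PCI within each treatment period" and "Incidence of clinical chemistry laboratory values of PCI within each treatment period". SAP 4.3.2.2.3 gives the display: "The haematology and clinical chemistry laboratory data, relative to PCI criteria, will be summarized by treatment group, laboratory test and category". SAP 4.3.2.2 fixes the base: "the denominator for percentages (N) will be the number of participants entering the associated treatment period".

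SAP 6.2.3 introduces the limits ("the following criteria will be used to flag potential clinical importance (for laboratory data, ECG parameters and vital signs")) and cautions that "a high abnormal or low abnormal laboratory value is not necessarily of clinical concern". The table in SAP 6.2.3.1 covers 27 analytes. Creatinine is flagged only on change from baseline. Haemoglobin and haematocrit have a change row in addition to an absolute one. The other 24 have absolute limits only.

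On entry, Protocol 5.2.2 exclusion 9 bars Grade 2 to 4 laboratory abnormalities "with the exception of creatine phosphokinase and lipid abnormalities" and ALT. Exclusion 6 tolerates isolated bilirubin above 1.5xULN when the direct fraction is below 35%.

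SAP 4.1.2 and Table 2 reset the baseline each period (Day 1, Day 4 and Day 15 predose). A footnote to the protocol's Schedule of Activities names Day 4 predose as the baseline for GSK3036656 dosing.

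**The concern.** Incidence within a period suggests something that arose in that period. As specified, the count is of participants whose value lies outside a limit in the period, whether or not it was outside before dosing. That is period prevalence.

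The practical cost is ambiguity. Suppose a test shows two flagged women of 20 under Microgynon alone and two of 20 under GSK3036656. They may be the same two women with long-standing values. Equally, one may have resolved and another newly arisen. The planned count cannot tell these apart, although the distinction is what a reader of a safety table wants.

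**Working it through.** **Inputs.** About 20 enrolled and 16 evaluable (Protocol 9.5, SAP 5); PCI limits (SAP 6.2.3.1); period boundaries (SAP 6.2.4); laboratory sampling days (Schedule of Activities); entry criteria (Protocol 5.2.2). The documents give no expected PCI rate, so the only stated figure to reproduce is the denominator: 16 / (1 − 0.20) = 20, which agrees.

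**Events per stable value.** Scheduled laboratory draws are predose on Days 1, 4 and 15, and on Day 18. Under SAP 6.2.4, Day 4 predose falls in Period 1, Day 15 predose in Period 2 and Day 18 in Period 3, so each period has one scheduled post-dose draw. A value that stays beyond an absolute limit is an event in 3 of 3 periods. One woman adds 1/20 = 5.0 percentage points per period (1/16 = 6.25 if 16 remain).

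**Entry limit against PCI limit.**

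| Test | Entry | PCI flag | Flagged at entry? |
|---|---|---|---|
| ALT | excluded above 1.5xULN | 3xULN or more | No |
| Haemoglobin | excluded below 80 g/L | below 75 g/L (low) | No |
| CPK | Grade 2 to 4 exempt | above 120 mcg/L | Yes |
| Total bilirubin | isolated above 1.5xULN tolerated by exclusion 6 | 1.5xULN or more | Yes, if exclusion 6 governs |
| RBC count | no named limit | below 4.2 million/mcL | Yes |

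**RBC row against haemoglobin row.** Haemoglobin (g/L) = RBC (million/mcL) × MCH (pg). The table leaves MCH unflagged from 27.5 to 33.2 pg.

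- At RBC 4.2: 4.2 × 27.5 = 115.5 g/L; 4.2 × 30.35 (mid-range) = 127.5 g/L; 4.2 × 33.2 = 139.4 g/L.
- At the haemoglobin limit of 75 g/L: 75 / 33.2 = 2.26 and 75 / 27.5 = 2.73 million/mcL.
- Example: haemoglobin 125 g/L with MCH 32 pg gives RBC 125 / 32 = 3.91. The "Red blood cell (RBC) count" row flags her; the haemoglobin and MCH rows do not.

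**How many women.** The share with a stable flagged value on a given test is not in the documents. Assume a share q, with women independent of one another. The expected number among 20 is 20q, and the chance of at least one is 1 − (1 − q)^20.

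| Assumed q | Expected of 20 | Chance of at least one |
|---|---|---|
| 2% | 0.4 | 33% |
| 5% | 1 | 64% |
| 10% | 2 | 88% |
| 20% | 4 | 99% |

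**Which baseline for Period 3.** Take a test unflagged on Days 1 and 4, then flagged on Days 15 and 18 without further change. Against the SAP's Day 15 baseline it is new in Period 2 but already present in Period 3. Against Day 4 it is new in both. A split using the SAP's period baseline would therefore remove from the combination period a change that arose on GSK3036656.

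**The case against.** Much of the defence stands. These are descriptive tables with no formal analysis, and the protocol's liver, QTc and haematology stopping rules do not use the PCI flags. SAP 4.4.1.1 already plans worst-case grade increase from baseline, change from period baseline, and normal-range shifts for ungraded tests. Microgynon alone is a within-participant reference, so a stable value appears in every column, which itself suggests no change. The Output and Programming Specification and the sponsor's data standards, which are not provided, may define a finer display.

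A reader might infer that a red-cell decline, the first GSK3036656 risk in protocol Table 2, would be buried under background RBC flags. The documents do not support that. Results are shown test by test, so RBC flags cannot hide haemoglobin, and falls of 25 g/L in haemoglobin or 0.075 in haematocrit from baseline have their own flags.

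A reader might also pool the narrow haematology rows into one large false-flag rate. The SAP specifies no pooled display, the coverage of the limits is unknown, and RBC, MCH and haemoglobin are arithmetically linked, so independence cannot be assumed.

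Deleting the narrow rows does not follow either. Reticulocytes belong to the named red-cell risk, and protocol Table 2 reports first-in-human reticulocytes against PCI criteria.

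The bilirubin example is conditional. Exclusion 9 does not exempt bilirubin, so admission depends on how exclusions 6 and 9 are reconciled, or on a compelling explanation with sponsor assent.

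What survives is that the additional summaries sit beside the named endpoint and leave its definition unchanged.

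**Conclusion.** The point holds as a minor interpretive fault. For 24 of 27 analytes, and for the absolute haemoglobin and haematocrit rows, the incidence endpoint counts values already present alongside new ones. Each stable flagged woman adds 5 percentage points per period at 20 participants, Microgynon alone included.

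This assumes that her value persists and that she is sampled in each period. The CPK route also assumes that the investigator does not exclude her on judgement under exclusion 7. The bilirubin route assumes that exclusion 6 governs. The RBC point rests on the SAP's own MCH and haemoglobin limits, because the laboratory's reference ranges are not in the documents. It shows that two rows of one table flag very different severities, not which limit is right. The number of women affected is unknown, and the shares tabulated above are assumptions. The primary pharmacokinetic analysis is unaffected.

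**What to change.** In SAP 4.3.2.2.3, show each laboratory PCI count by test and period on three lines: total, as now planned; new or worsened since baseline; already PCI at baseline and not worsened. Keep the denominator.

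- **Baseline.** Use Day 1 predose for Period 1 and Day 4 predose for Periods 2 and 3, in line with the protocol's footnote. State that this table departs from SAP Table 2 for Period 3.
- **Worsening.** Define it in advance, for example as a higher CTCAE grade in the flagged direction where the test is gradable, and a prespecified further change where it is not. Otherwise a large rise from an already flagged value would not be separated from a stable one.
- **Missing baseline.** Say on which line such values fall.
- **Rows.** Keep all of them, including reticulocytes. Reconcile the RBC row with the haemoglobin row in SAP 6.2.3.1 so that they flag comparable severity.
- **Entry criteria.** Reconcile exclusions 6 and 9 on bilirubin.

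The table change costs SAP wording and programming, longer tables, and a footnote explaining the second baseline convention. Reconciling the exclusions needs protocol wording. Data collection, sample size and the primary analysis do not change.
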